7.4. Variables

7.4.1 Baseline Data Collection (Day 0)

Baseline data including:

- Demographic data
date of birth, height, weight, race and ethnicity

- Medical history
 - Immunization and viral infections (HIV, vaccination hepatitis A/B, hepatitis A/B/C)
- Medication history
 - Concomitant diseases and medications including factor IX and other factor IX-containing blood products
- Hemophilia History
 1. Date of the diagnosis of hemophilia B
 2. Age of first exposure to PCC, FFP or any other coagulation factor products
 3. Disease severity
 4. Genetic mutation (if available)
 5. Inhibitor history
 6. FIX hypersensitivity allergic reactions
 7. Family history of hemophilia and inhibitor
 8. Approximate number of exposure days to Factor IX products (e.g. plasma-derived FIX or BeneFIX) that the patient has experienced.
 9. Treatment [prophylaxis regimen (dose and frequency) or on-demand treatment] at the time of enrollment

7.4.2 Treatment Data Collection (Day 0 to 12 months/Early Withdrawal)

All data will be collected in the CRF. This data will be collected following Day 0 through the Registry Completion/Early Withdrawal Visit.

1. Exposure days, bleed, infusion and response data will be collected throughout the treatment period on the subject diaries.
2. The efficacy outcomes data will be:
 - Annualized bleeding rates (ABR) in subjects receiving treatment with BeneFIX,
 - The responses to all on-demand treatment with BeneFIX for all bleeds (4 point scale of assessment),
 - Number of BeneFIX infusions to treat each new bleed
 - Number of spontaneous/non traumatic breakthrough bleeds within 48 hours of a prophylaxis dose of BeneFIX

7.4.3 Safety Data Collection (Day 0 to 12 months/Early Withdrawal)

Safety data collected throughout the treatment period (Day 0 to 12 months/Early Withdrawal) will consist of:

- All AE and SAE data, including product-related medically important adverse events (inhibitor development, FIX hypersensitivity allergic reactions, thrombogenicity, lack of effect and red cell agglutination,). This data will be reported on the appropriate CRF and AEM forms during treatment with BeneFIX.

- Laboratory results determining the presence of FIX inhibitor antibodies by the Bethesda assay or Nijmegen modification of the Bethesda assay are recommended to be collected for subjects at all study visits.
- Changes in concomitant diseases or medicinal therapy
 1. Medicinal concomitant therapy
- FIX activity and recovery values, if available and assessed at routine clinic visits.

7.5. Data sources

Investigator will first record the study data in source documents, such medical records through subject's scheduled visits. Investigator or the delegate will then enter the study data as well as subject's diary data onto the eCRFs in the Electronic Data Collection (EDC) system.

7.6. Study size

The registry study will be conducted in hospitals and clinics in China. Since the number of potential subjects is unknown, the study is not designed based on sample size considerations.

7.7. Data management

Datalabs is the Electronic Data Collection (EDC) system for the study. The statistical software is Statistical Analysis System(SAS).

The investigator is responsible to collect study data, including the eCRF data, laboratory data and the subject's diary data, via the EDC system in a timely manner and to ensure the integrity, accuracy, and completeness of the data.

The investigator should keep accurate records of: identity of all subjects (sufficient information to link the patients to the corresponding study data), serious adverse event forms, all related source documentation, details of treatment disposition, as well as relevant correspondence details (e.g. letters, emails, meeting minutes, telephone call reports). The investigator record retention period should comply with the local regulations, or as specified in the Clinical Study Agreement, whichever is longer.

If the investigator becomes unable for any reason to continue to retain study records for the required period (e.g., retirement, relocation), Pfizer should be notified. The study records must be transferred to a designee acceptable to Pfizer, such as another investigator, another institution, or to an independent third party arranged by Pfizer. The investigator must obtain Pfizer's written permission before disposing of any records, even if retention requirements have been met.

7.8. Data analysis

Detailed methodology for summary and statistical analyses of data collected in this study will be documented in a Statistical Analysis Plan (SAP), which will be dated, filed and maintained by the sponsor. The SAP may modify the plans outlined in the protocol; any major modifications of primary endpoint definitions or their analyses would be reflected in a protocol amendment.

A statistical sample size calculation will not be performed for this study. Because all eligible and willing-to-participate subjects will be enrolled in the study and no statistical hypotheses are tested.

All safety and efficacy analyses, except the analysis for Annualized Bleeding Rates (ABR), will be performed on all subjects who receive at least one dose of BeneFIX. ABR analysis will be performed on subjects who participated in prophylaxis period for at least 6 months.

The primary safety outcomes to be reported will be development of clinically significant FIX inhibitors, FIX hypersensitivity allergic reactions, thrombogenicity, lack of effect and red cell agglutination.

Secondary safety outcomes include the frequency of adverse events and serious adverse events, etc.

Secondary efficacy outcomes will be:

- Annualized bleeding rates (ABR) in subjects receiving treatment with BeneFIX,
- The responses to all on-demand treatment with BeneFIX for all bleeds (4 point scale of assessment),
- Number of BeneFIX infusions to treat each new bleed,
- Number of spontaneous/non traumatic breakthrough bleeds within 48 hours of a prophylaxis dose of BeneFIX.

The efficacy results of this study will be presented using descriptive statistics. The following descriptive statistics will be used:

- For numeric endpoints: sample size, mean, standard deviation, median, minimum and maximum;
- For categorical endpoints: count and percentage.

Safety data will be tabulated and listed according to Pfizer's standard reporting algorithms. The reasons for discontinuation of BeneFIX therapy will be described.

Subgroup analysis will be done by several sub-populations.

Additional details of the analysis will be provided in the statistical analysis plan and/or the clinical study report. This information may include details of missing and, if applicable, unused and spurious data. Deviations from the statistical plan will be reported in the clinical study report.

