1. LIST OF ABBREVIATIONS

Abbreviation	Definition
AE	Adverse Event
AEM	Adverse Event Monitoring
BU	Bethesda Unit(s)
CRF	Case Report Form
ED	Exposure Day
eCRF	Electronic Case Report Form
FFP	Fresh Frozen Plasma
HIV	Human Immunodeficiency Virus
ICH	International Conference on Harmonisation
IRB/IEC	Institutional Review Board/Independent Ethics Committee
IU	International Units
IV	Intravenous
MTP	Minimally Treated Patients
PCC	Prothrombin Complex Concentrates
PTP	Previously Treated Patients
PUP	Previously Untreated Patients
SAE	Serious Adverse Event
CFDA	State Food and Drug Administration

Term	Definition
AEM form	Adverse Event Monitoring form
Bleeding episode	Hemorrhage occurring spontaneously or due to injury at 1 or more sites.
Completed subject	Any subject who completes the registry activities through the Registry Completion Visit and who is not withdrawn early.
Cryoprecipitate	Prepared from plasma and contains fibrinogen, von Willebrand factor, factor VIII, factor XIII and fibronectin.
Exposure day	Any calendar day during which the subject receives BeneFIX or other purified human derived FIX product. This excludes FFP, PPC and cryoprecipitate.
Factor IX inhibitor (clinically significant)	Local positive inhibitor and at least one of the following observations within 4 weeks before or 4 weeks following a positive inhibitor result: 
 1. ≥ 2 events indicating a decrease in the efficacy of BeneFIX (or other AE indicating a decrease in the efficacy of the test article) 2. A need to administer alternate hemostatic products or increase the dose or dosing frequency in order to achieve sufficient efficacy
Factor IX inhibitor (local)	A local positive result using either the Bethesda assay (≥ 0.6 BU or $>$ the upper limit of normal) or the Nijmegen modification of the Bethesda assay (≥ 0.6 BU).
Factor IX inhibitor (history of)	A history of factor IX inhibitor (clinical or laboratory-based assessment).
FIX Hypersensitivity Allergic reaction	A hypersensitivity reaction to BeneFIX with symptoms including hives, generalized urticaria, tightness of the chest, wheezing, hypotension, and anaphylaxis.
Fresh Frozen Plasma	Plasma removed from whole blood that involves freezing during the preparation. It contains all coagulation factors in normal concentrations.
Incremental recovery	FIX:C at 30 minutes after infusion, [IU/dL]/[IU/kg]

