7.3 Study procedures

A written, Pfizer and institutional review board (IRB)/independent ethics committee (IEC)-approved, informed consent/assent (as appropriate) must be obtained before initiating study procedures.

Informed consent must be obtained from the legal representative of the child or adolescent in accordance with local law before assent is sought. An assent should be obtained from all subjects that have an intellectual age of 7 years or more. All potential pediatric subjects should be informed to the fullest and most appropriate extent possible about the study, in language and terms they are able to understand.

If a subject signed assent for a study, a consent must be signed once the subject turns legal age, based on local requirements.

The eligibility of the subject will be evaluated. After inclusion of the subject and after obtaining written informed consent (prior to any registry-related procedure being performed) from the subject's parents/caregiver/legal representative and assent, if applicable, the investigator or site staff will enter the subject data into source documents and into an electronic Case Report Form (eCRF).

Following the baseline data collection (Day 0), the visits to collect registry study data are at the discretion of the investigator and may follow the local usual standard of care, however, the sponsor recommends safety, treatment data and FIX inhibitor assessments at 6 month intervals at a minimum during the 1 year of participation in the registry. A Follow-up Call is to be conducted at least 28 calendar (+10 days) after the Final/Early Termination visit in order to collect information on the occurrence of adverse events and concomitant medications.

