8.2 Patient withdrawal

Patients may withdraw from the study at any time at their own request, or they may be withdrawn at any time at the discretion of the investigator or sponsor for safety, behavioral, or administrative reasons. In any circumstance, every effort should be made to document patient outcome, if possible. The investigator should inquire about the reason for withdrawal and follow-up with the patient regarding any unresolved adverse events.

For patients that are withdrawn from the study prior to the 12 month visit, the treatment and safety data are to be collected at that visit and it is recommended to collect a FIX Inhibitor sample that is analyzed at the local laboratory. A Follow-up Call is to be conducted at least 28 calendar (+10 days) after the Final/Early Termination visit in order to collect information on the occurrence of adverse events and concomitant medications. If the patient withdraws from the study, and also withdraws consent for disclosure of future information, no further evaluations should be performed, and no additional data should be collected. The sponsor may retain and continue to use any data collected before such withdrawal of consent.

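### A single all-dosed figure for the primary inhibitor outcome mixes subjects who tested negative with subjects never tested, because inhibitor assays are only recommended and none is required at entry

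*Protocol*

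**What the plan says.** **Population.** Protocol section 7.8 states that safety and efficacy analyses, with ABR as the only exception, "will be performed on all subjects who receive at least one dose of BeneFIX". The same section lists the primary outcomes, inhibitors first: "The primary safety outcomes to be reported will be development of clinically significant FIX inhibitors".

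**Case definition.** The definitions in section 1 make an assay necessary for a clinically significant inhibitor: "Local positive inhibitor and at least one of the following observations within 4 weeks before or 4 weeks following a positive inhibitor result". The accompanying observation is either two or more events pointing to reduced efficacy, or a need for other haemostatic products or more intensive dosing.

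**Testing on study.** Under section 7.4.3, inhibitor results "are recommended to be collected for subjects at all study visits". Under section 7.3, after Day 0 "the visits to collect registry study data are at the discretion of the investigator", although "the sponsor recommends safety, treatment data and FIX inhibitor assessments at 6 month intervals at a minimum". For early withdrawals, section 8.2 says "it is recommended to collect a FIX Inhibitor sample that is analyzed at the local laboratory".

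**Testing at entry.** The Day 0 list in section 7.4.1 has "Inhibitor history" but no assay. Exclusion 4 (section 7.2.4) bars a past or current inhibitor and gives a titer threshold for laboratory assessments, without requiring that one be done. Inclusion 2 (section 7.2.3) admits patients already using BeneFIX.

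**The concern.** A dosed subject with no inhibitor result after Day 0 is in the population for the outcome but cannot become a case. He is counted in the same way as a subject who was tested and found negative. A reader given one all-dosed percentage cannot tell how much of it rests on negative assays and how much on missing ones.

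The second gap is at entry. A current user whose inhibitor was never recognised can enrol, have a first assay during follow-up, and be recorded as having developed an inhibitor on study.

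Inhibitor development is the first-listed primary outcome of a safety registry. What is at stake is how its rate, or an absence of cases, can be read. No hypothesis is tested, so type I error and power are not affected.

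**Working it through.** The protocol gives no expected inhibitor rate, testing rate or sample size, so there is no stated figure to reproduce. All numerical inputs below are assumptions, used to show direction and range.

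**1. Effect of incomplete testing**

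Notation:
- p = true incidence of the outcome
- f = share of dosed subjects tested after Day 0
- s = share of true cases who are tested

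Then:
- rate over all dosed = p × s
- rate over tested subjects = p × s / f

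With p = 5%:

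| f | s | All dosed | Tested only |
|---|---|---|---|
| 80% | 80% (unrelated to risk) | 0.05 × 0.8 = 4.0% | 5.0% |
| 60% | 60% (unrelated to risk) | 0.05 × 0.6 = 3.0% | 5.0% |
| 40% | 40% (unrelated to risk) | 0.05 × 0.4 = 2.0% | 5.0% |
| 60% | 80% (partly symptom-driven) | 0.05 × 0.8 = 4.0% | 0.04 / 0.6 = 6.7% |
| 80% | 100% (every case tested) | 5.0% | 0.05 / 0.8 = 6.3% |
| 60% | 100% (every case tested) | 5.0% | 0.05 / 0.6 = 8.3% |
| 40% | 100% (every case tested) | 5.0% | 0.05 / 0.4 = 12.5% |

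If testing is unrelated to risk (s = f), the tested-only rate is right and the all-dosed rate is low. If every true case is tested (s = 1), the all-dosed rate is right and the tested-only rate is high. For s between f and 1, p × s ≤ p ≤ p × s / f, so the two rates bracket the truth. The bracket fails if true cases are tested less often than other subjects (s below f).

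**2. No cases observed**

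The exact (Clopper-Pearson) two-sided 95% upper limit with 0 cases in n is 1 − 0.025^(1/n). For an assumed 100 dosed subjects:
- n = 100: 3.6%
- n = 80 tested: 4.5%
- n = 60 tested: 6.0%
- n = 40 tested: 8.8%

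The 3.6% limit is justified only if any case among the untested would have come to light. The others apply if the tested subjects represent all dosed subjects.

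**3. Inhibitors present at entry**

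Let q be the share entering with an unrecognised inhibitor that later meets the case definition, with everyone tested on study. The apparent rate of new cases is q + (1 − q) × p. With p = 1%:
- q = 0.5%: 0.005 + 0.995 × 0.01 = 1.5%, of which 33% was present at entry
- q = 1%: 0.01 + 0.99 × 0.01 = 2.0%, of which 50% was present at entry
- q = 2%: 0.02 + 0.98 × 0.01 = 3.0%, of which 67% was present at entry

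This error raises the reported rate. Incomplete testing can only lower the all-dosed rate or leave it unchanged. The two can offset each other.

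**The case against.** The strongest reply is that the primary outcome is not simply a positive assay. It also needs signs of treatment failure, and those signs are a plausible reason to order an assay. A silent inhibitor in an untested subject is not a primary case at all. Lack of effect is itself a primary outcome, reported on the same terms as an SAE (section 9.2), so part of the clinical signal is captured without an assay. This stands. A reader might infer that the all-dosed rate must understate incidence, but the documents do not support that, because nothing in them says who will be tested.

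A reader might also infer that tested subjects should become the main denominator. That does not follow either: if testing follows symptoms, the table shows a tested-only rate can be well above the truth.

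On entry, exclusion 4 removes known inhibitors, exclusion 6 removes patients whose history is inadequate to establish eligibility, and there is a screening review (section 7.1). Section 7.4.3 can be read as recommending an assay at Day 0 too. Only unrecognised inhibitors remain, and their number is unknown. Nor are the visits themselves optional in every sense: a completion or early-withdrawal visit is named, and it is the assay that is left open, as suits a non-interventional design.

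Finally, section 7.8 attaches counts and percentages to the efficacy results and sends safety data to the sponsor's standard reporting rules, so the percentage is inferred from the stated population. The SAP, not available here, may add a tested subset. But the protocol is not silent: it sets one population, makes an outcome-specific exception for ABR and makes none for inhibitors. It also says that major changes to primary endpoint analyses would need an amendment.

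**Conclusion.** The point holds as a limit on what the inhibitor figure can show. As section 7.8 stands, never-tested subjects are counted with those who tested negative, and an inhibitor unrecognised at entry can be counted as new. The net direction of bias cannot be determined from the documents.

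The size depends on testing. For an assumed true 5% and 40% to 80% tested, the all-dosed rate lies between 2% and 5%, and the tested-only rate between 5% and 12.5%, for s from f to 1. With no cases in 100 dosed, the 95% upper limit could be 3.6% or as high as 8.8% on the same range of testing.

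A further inference, that the figure could not be compared with other registries, has no basis in the documents. This is a cheap and worthwhile improvement to the reporting of a primary outcome. It does not show that the all-dosed population is wrong.

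**What to change.** In section 7.8, keep the all-dosed percentage and add, for the inhibitor outcome only:

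1. The percentage among dosed subjects with no positive inhibitor result at or before Day 0 and at least one result after Day 0.
2. The numbers tested at baseline, tested on study and never tested.
3. A separate listing of any first positive in a subject without a documented negative result at or before Day 0.
4. A statement that the two rates rest on different assumptions: the all-dosed rate is right if every true case is tested, the tested-subject rate if testing is unrelated to risk.

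The other primary events can keep the all-dosed population alone.

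The cost is a few lines of text, one table column and one listing, with no additional test or visit. The downside is a second rate to explain, usually higher and less precise because its denominator is smaller.

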7. RESEARCH METHODS

7.1. Study design

This is a non-interventional, voluntary prospective registry study conducted in major hemophilia treatment centers in China. The registry will enroll Chinese patients with Hemophilia B of all severities. Patients will undergo a screening review prior to enrollment. Enrolled subjects will be treated with intravenous infusions of BeneFIX at a dose and frequency prescribed by the subject's treating physician in accordance with the BeneFIX label and will be adjusted solely according to medical and therapeutic necessity. The registry study will capture observations that will be used for evaluating recombinant FIX replacement product safety, including: subject demographics, medical history, hemophilia history and medications. Safety assessments, treatment data and any laboratory-based FIX inhibitor determinations will be collected at all visits. It is recommended that all subjects in this registry study will be followed for a minimum of 6 months and participation in this registry study will conclude after 12 months.

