7.2.3 Inclusion criteria

Patients must meet all of the following inclusion criteria to be eligible for inclusion in the study:

1. Male subjects of all ages and severity with Hemophilia B.
2. Subjects using or intending to use BeneFIX for Factor IX replacement therapy.
3. Subjects/parents/legal representatives must be able to comply with registry procedures (informed consent/assent process, clinical visits, reporting of infusion and bleed data, reporting of adverse events, etc).
4. Evidence of a personally signed and dated informed consent document indicating that the patient (or a legally acceptable representative) has been informed of all pertinent aspects of the study.

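### Section 7.8 limits the ABR analysis to subjects with at least 6 months in an undefined prophylaxis period, which is narrower than the outcome it reports and selects on post-enrolment treatment duration

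*Protocol*

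**What the plan says.** The efficacy outcomes in Protocol section 7.4.2, repeated as secondary efficacy outcomes in section 7.8, begin with "Annualized bleeding rates (ABR) in subjects receiving treatment with BeneFIX". Neither list adds a condition on regimen or on time treated.

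Section 7.8 then sets the analysis populations. Every safety and efficacy analysis other than ABR "will be performed on all subjects who receive at least one dose of BeneFIX". ABR is the one named exception: "ABR analysis will be performed on subjects who participated in prophylaxis period for at least 6 months". No reason is given. The definitions in section 1 cover prophylaxis and the treatment period (Day 0 to completion or withdrawal), but not a prophylaxis period.

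Four other provisions matter here:

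- Eligibility does not depend on regimen. Section 7.2.3 admits "Subjects using or intending to use BeneFIX for Factor IX replacement therapy", and section 7.4.1 records "Treatment [prophylaxis regimen (dose and frequency) or on-demand treatment] at the time of enrollment".
- Bleeds are collected from everyone. Section 7.4.2 says "Exposure days, bleed, infusion and response data will be collected throughout the treatment period on the subject diaries".
- Follow-up is short, and its minimum is only a recommendation: subjects should be "followed for a minimum of 6 months and participation in this registry study will conclude after 12 months" (section 7.1).
- Patients may leave, or be withdrawn, at any time (section 8.2), and they are not replaced (section 7.2.1).

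**The concern.** There are two separate problems.

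The first is one of definition. The outcome is named for subjects treated with BeneFIX, but the number will come from a subset defined by regimen and duration. The registry sets out to describe usual treatment in China (section 5). A table headed with the outcome's name would not describe that population, and patients treated only on demand would have no bleeding rate at all. Since the prophylaxis period is undefined, it is also unclear how interrupted prophylaxis, or a switch between regimens, counts towards the 6 months.

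The second is selection. Whether a subject reaches 6 months of prophylaxis is known only after enrolment, and bleeding may itself influence it. A patient who gives up prophylaxis at month 3 because he keeps bleeding leaves the ABR set for a reason tied to the outcome. If that pattern exists, the reported ABR describes those who did well enough to stay on, and readers would take it as the rate under prophylaxis.

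**Working it through.** The protocol states no expected ABR, regimen mix, dropout rate or sample size, so there is no figure to reproduce. The check has three parts: a reading of who is excluded, a simple calculation, and a simulation. Every numerical input below is an assumption.

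**1. Who contributes no ABR under section 7.8 as written**

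- A subject treated only on demand, however long he is followed.
- A subject who starts prophylaxis after month 6 of the 12-month participation, since fewer than 6 months remain.
- A subject who stops prophylaxis, moves to on-demand treatment or withdraws before 6 months of prophylaxis.

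A subject who starts on demand and later accrues 6 months of prophylaxis does enter.

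If 30% to 90% of dosed subjects are on demand only, and 20% of the rest stop prophylaxis early, the ABR set is 0.70 × 0.80 = 56% down to 0.10 × 0.80 = 8% of dosed subjects.

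**2. Simple calculation among prophylaxis subjects**

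Let a fraction p stop at 3 months (0.25 year) with rate r, while the rest continue for 1 year with rate 4. The planned set reports 4.0. The pooled rate over all observed prophylaxis time is

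pooled = [(1 − p) × 1 × 4 + p × 0.25 × r] / [(1 − p) × 1 + p × 0.25]

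| p | r | Pooled rate | Planned figure below pooled |
|---|---|---|---|
| 10% | 8 | (3.6 + 0.2) / 0.925 = 4.11 | 1 − 4/4.11 ≈ 3% |
| 20% | 12 | (3.2 + 0.6) / 0.85 = 4.47 | 1 − 4/4.47 ≈ 11% |
| 30% | 12 | (2.8 + 0.9) / 0.775 = 4.77 | 1 − 4/4.77 ≈ 16% |

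**3. Simulation of the mechanism**

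This used 400,000 prophylaxis subjects. Individual ABR followed a gamma distribution with mean 4 and shape 1. The monthly stopping hazard was a + b × own ABR, and follow-up was censored at 12 months. The realised true mean was 3.99.

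| a | b | Excluded by 6-month rule | Mean ABR, 6-month set | Pooled rate, all subjects | Rate in excluded subjects |
|---|---|---|---|---|---|
| 0.02 | 0 | 11.3% | 3.99 | 3.99 | 3.95 |
| 0.01 | 0.005 | 15.9% | 3.56 | 3.60 | 6.13 |
| 0.01 | 0.01 | 24.1% | 3.22 | 3.32 | 6.11 |
| 0.01 | 0.02 | 36.4% | 2.69 | 2.92 | 5.75 |

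When stopping is unrelated to bleeding (first row), the restriction costs subjects but causes no bias. When stopping rises with bleeding, the 6-month mean falls below the true mean by (3.99 − 3.56)/3.99 = 11%, then 19% and 33%. Pooling all time moves the estimate the right way but recovers little: in the third row it goes from 3.22 to 3.32 against a true 3.99. High bleeders who stop early still contribute little time.

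**The case against.** The restriction is explicit. Section 7.8 exempts ABR from the general analysis set on purpose, and the outcome list can be read as a label that the next rule narrows. A minimum observation time is also a recognised safeguard when subject-level ABRs are summarised by mean and median: over 3 months, a single bleed changes a subject's ABR by 1/0.25 = 4 per year. This stands as a reason to keep the 6-month subset. It does not justify making that subset the only ABR analysis, and a minimum observation time does not require leaving out on-demand subjects.

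Early failures are not lost to the study. Inhibitors, hypersensitivity, lack of effect, thrombogenicity and red cell agglutination are primary outcomes analysed in all dosed subjects. So are breakthrough bleeds within 48 hours of a prophylaxis dose, and reasons for discontinuing BeneFIX will be described. This limits the consequence, but none of it supplies a bleeding rate.

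Section 7.8 also lets the SAP modify the plan, and the SAP is not at hand. It may already add ABR summaries. The restriction is nevertheless fixed in the protocol as it stands.

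A reader might infer more than the text supports:

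- *That the reported ABR is biased low.* The protocol says nothing about why patients stop. If stopping is unrelated to bleeding there is no bias; if patients with few bleeds leave prophylaxis, the direction reverses.
- *That the outcome is defined for all treated subjects, or that every on-demand patient is dropped.* The outcome wording does not say all, and a later 6 months of prophylaxis brings a subject in.
- *That the understatement reaches 29% or 38%.* Those figures compare 4.0 with an unweighted mean of subject ABRs (0.8 × 4 + 0.2 × 12 = 5.6, or 0.7 × 4 + 0.3 × 12 = 6.4). That mean gives a 3-month subject the same weight as a 12-month subject, which is the unstable summary that a minimum duration is meant to avoid. Against the pooled rate, the same inputs give 11% and 16%.

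**Conclusion.** The point holds in a limited form. The outcome's name and its analysis set describe different populations, the period that governs entry is undefined, and collected bleed data from subjects without 6 months of prophylaxis go unused for ABR. These follow from the text alone.

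The bias is conditional: downward if heavier bleeders stop early, absent only if stopping is unrelated to bleeding. Its size cannot be known from the protocol. With 10-30% stopping at 3 months and an ABR of 8-12 against 4 in those who continue, the planned figure lies about 3-16% below the pooled rate. The shortfall from the true mean can be larger when stopping depends strongly on bleeding, as the simulation shows, but that too rests wholly on assumed inputs.

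ABR is one of four secondary, descriptive efficacy outcomes. No hypothesis test, sample size or primary safety outcome depends on it. The change is worth making because it is cheap and ABR will be read as a summary of bleeding on the product.

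**What to change.** In section 7.8, replace the ABR analysis-set sentence so that:

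- ABR is reported for all dosed subjects with diary time, separately for prophylaxis time and on-demand time, as total bleeds over total observed time. The 95% confidence interval should allow for over-dispersion, for example from a negative binomial model with log time as offset.
- The prophylaxis period is defined, including its start, its end, and how interruptions and regimen switches are counted.
- The subset with at least 6 months of prophylaxis is kept as a sensitivity analysis, with the descriptive summaries already planned.
- The number of subjects that subset excludes, the reasons, and their bleed rate are reported.

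No new data are needed. The diaries already hold bleeds and infusions, and the planned breakthrough-bleed outcome already requires prophylaxis doses to be identified. The cost is slightly more analysis work, a small addition to the descriptive-statistics text to allow the interval, and a possibly less favourable ABR. Since pooling does not fully remove selection, the report should say so and show the excluded subjects' rate beside the main result.
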